The drop-out rate over the 3 years of the safety and efficacy stage of the study (Stage 1) is estimated to be 27% ( $\sim$ 10% per year). As long as this drop-out rate is not exceeded, then at least 150 subjects (300 eyes) receiving the higher concentration (0.02% atropine) will be available for the evaluation of safety.

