#### **Study Procedures:**

Office Visits should occur within  $\pm 2$  weeks of the expected visit date.

Screening/Randomization/Baseline Visit (Day 0): Sites should complete screening/randomization/baseline procedures and enroll subjects within 30 days from signing the informed consent.

The clinical site will obtain signed informed consent from the parent or legal guardian of the subject and assent from the subject (as applicable). The subject will then undergo screening evaluations to determine eligibility for the study which will include review of medical/ocular and prior medication history, a urine pregnancy test for female subjects of childbearing potential, heart rate (HR), monocular Best-Corrected Visual Acuity (BCVA) measurement at distance and near, photopic pupil size measurement, slit-lamp examination (SLE) (check for narrow angles), tonometry, dilated fundus examination and cycloplegic autorefraction. Height and weight will also be assessed.

Following confirmation of eligibility, the clinical site will measure axial length and, if possible, crystalline lens thickness. The site will access the IRT, which will assign the subject to 1 of the 3 treatment arms and assign the initial study medication kit to be dispensed to the parent/guardian following instruction on administration.

One (1) drop of the study medication will be administered into each eye QD, at bedtime. Because AEs are to be collected beginning after signing of informed consent/assent, the site will document any events that may be volunteered spontaneously by the subject or parent/guardian that occur before the end of the visit.

If the subject requires initial or new spectacles/contact lenses (applicable if the refraction reveals at least -0.50 D myopic progression and/or if the eye care practitioner deems it clinically necessary to improve vision), the site will provide a refractive prescription and lenses/frames (if needed) or soft contact lenses.

All screening evaluations will serve as baseline measurements.

Stage 1 Telephone Checks – (Months 1, 2, 4.5, 7.5, and 10.5): Sites will contact the subject or their parent/guardian by telephone at the end of Month 1 and Month 2 and then midway between office visits during the initial year of the study to collect information regarding AEs and treatment adherence. Telephone checks can be continued or reinstated at any time during the study to assist with maintaining protocol and treatment adherence.

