#### **Primary Efficacy Endpoint:**

The primary efficacy endpoint is the between-treatment group (Atropine Sulfate Ophthalmic Solution, 0.02% versus Vehicle) difference in the proportion of subjects who show < -0.50 D myopia progression (SER) at the Month 36 visit.

The primary and all secondary endpoints comprise a fixed sequence set of endpoints to be tested in order. A 2-sided significance level of 0.05 will be adopted.

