### 4.3. Tertiary Endpoints

Tertiary endpoints will consist of:

1. Between-treatment group (Atropine Sulfate Ophthalmic Solution, 0.02% versus Vehicle) difference in the proportion of subjects' eyes who show less than 0.5 D myopia progression (SER) from baseline at the Month 24 and Month 12 visits.
2. Between-treatment group (Atropine Sulfate Ophthalmic Solution, 0.02% versus Vehicle) difference in the mean change from baseline in SER at the Month 24 and Month 12 visits.
3. Between-treatment group (Atropine Sulfate Ophthalmic Solution, 0.01% versus Vehicle) difference in the proportion of subjects' eyes who show less than 0.5 D myopia progression (SER) from baseline at the Month 24 and Month 12 visits.
4. Between-treatment group (Atropine Sulfate Ophthalmic Solution, 0.01% versus Vehicle) difference in the mean change from baseline in SER at the Month 24 and Month 12 visits.
5. Between-treatment group (Atropine Sulfate Ophthalmic Solution, 0.02% versus Vehicle) difference in the proportion of subjects' eyes who show less than 0.75 D myopia progression (SER) from baseline at the Month 36 visit.
6. Between-treatment group (Atropine Sulfate Ophthalmic Solution, 0.01% versus Vehicle) difference in the proportion of subjects' eyes who show less than 0.75 D myopia progression (SER) from baseline at the Month 36 visit.

This document is confidential.

7. Between-treatment group (Atropine Sulfate Ophthalmic Solution, 0.02% versus Vehicle) difference in the time to change from baseline in myopia of -0.75 D SER.
8. Between-treatment group (Atropine Sulfate Ophthalmic Solution, 0.01% versus Vehicle) difference in the time to change from baseline in myopia of -0.75 D SER
9. Between-treatment group (Atropine Sulfate Ophthalmic Solution, 0.02% versus Vehicle) difference in the mean number of new prescriptions given after the start of treatment due to progression through the Month 36 visit.
10. Between-treatment group (Atropine Sulfate Ophthalmic Solution, 0.01% versus Vehicle) difference in the mean number of new prescriptions given after the start of treatment due to progression through the Month 36 visit.
11. Between-treatment group (Atropine Sulfate Ophthalmic Solution, 0.02% versus Vehicle) difference in the proportion of subjects who progressed from baseline to high myopia (SER -6.00 D or more myopic) at the Month 36 visit.

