8.3.9. Between-treatment Group (Atropine Sulfate Ophthalmic Solution, 0.02% versus Vehicle)  
Difference in the Number of New Prescriptions Given After the Start of Treatment Due to Progression through the Month 36 visit

A tertiary analysis will be performed on the between-treatment group (Atropine Sulfate Ophthalmic Solution, 0.02% versus vehicle) difference in the number of new prescriptions given after the start of treatment due to progression through the Month 36 visit. The analysis method will be performed using the Cochran-Mantel-Haenszel row mean scores (ANOVA) statistic using the statement.

```
proc freq data=xxxx;  
  tables Treatment*Prescriptions /cmh noprint;  
run;
```

Summary statistics will be presented along with a full data listing by treatment group.

This document is confidential.

8.3.10. Between-treatment Group (Atropine Sulfate Ophthalmic Solution, 0.01% versus Vehicle) Difference in the Number of New Prescriptions Given After the Start of Treatment Due to Progression through the Month 36 visit

A tertiary analysis will be performed on the between-treatment group (Atropine Sulfate Ophthalmic Solution, 0.01% versus vehicle) difference in number of new prescriptions given after the start of treatment due to progression through the Month 36 visit. The analysis method will be performed using the Cochran-Mantel-Haenszel row mean scores (ANOVA) statistic using the statement.

```
proc freq data=xxxx;  
  tables Treatment*Prescriptions /cmh noprint;  
run;
```

Summary statistics will be presented along with a full data listing by treatment group.

8.3.11. Between-treatment Group (Atropine Sulfate Ophthalmic Solution, 0.02% Versus Vehicle) Difference in the Proportion of Subjects who Progressed to High Myopia (SER -6.00 D or more myopic) at the Month 36 Visit

A tertiary analysis will be performed on the between-treatment group (Atropine Sulfate Ophthalmic Solution, 0.2% versus vehicle) difference in the proportion of subjects who progressed to high myopia (SER -6.00 D or more myopic) at the Month 36 visit. Progression to high myopia is defined as either of a subject's eyes progressed to high myopia at any time during a visit window. The analysis method will be the same as the analysis as described in 8.3.12 below. Results will be presented as overall results and by baseline myopia stratification.

Summary statistics will be presented along with a full data listing by treatment group.

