14.2.2		Secondary Efficacy Parameters	
14.2.2.1		Change from Baseline in Normalized SER	
	14.2.2.1.1	Analysis of the Change from Baseline in Normalized SER (D) in Stage 1 by Treatment Group and Visit Mixed Effect Model	Stage 1 Modified Intent-to-Treat Set
	14.2.2.1.4	Analysis of the Change from Baseline in Normalized SER (D) in Stage 1 by Treatment Group and Visit Mixed Effect Model	Stage 1 Intent-to-Treat Set

This document is confidential.

Header	Table Number	Name	Analysis Set
	14.2.2.1.7	Summary of the Change from Study Baseline in Normalized SER (D) by Stage, Treatment Group and Visit	Modified Intent-to-Treat Set
	14.2.2.1.8	Summary of the Change from Study Baseline in Normalized SER (D) by Stage, Treatment Group and Visit	Intent-to-Treat Set
14.2.2.2		Change from Baseline in Axial Length at Month 36	
	14.2.2.2.1	Analysis of the Change from Baseline in Axial Length (mm) in Stage 1 by Treatment Group and Visit Mixed Effect Model	Stage 1 Modified Intent-to-Treat Set
	14.2.2.2.4	Analysis of the Change from Baseline in Axial Length (mm) in Stage 1 by Treatment Group and Visit Mixed Effect Model	Stage 1 Intent-to-Treat Set
14.2.3		Tertiary Efficacy Parameters	
14.2.3.1		Proportion of Subjects' Eyes who Show less than 0.75 D Myopia Progression (Normalized SER) from Baseline	
	14.2.3.1.1	Analysis of the Proportion of Subjects' Eyes who Show less than 0.75 D Myopia Progression (Normalized SER) from Baseline in Stage 1 by Treatment Group and Visit Mixed Effects Model	Stage 1 Modified Intent-to-Treat Set
	14.2.3.1.3	Analysis of the Proportion of Subjects' Eyes who Show less than 0.75 D Myopia Progression (Normalized SER) from Baseline in Stage 1 by Treatment Group and Visit Mixed Effects Model	Stage 1 Intent-to-Treat Set
14.2.3.2		Time to Change in Myopia of -0.75 D Normalized SER	
	14.2.3.2.1	Analysis of Time to Change from Baseline in Myopia Progression of -0.75 D Normalized SER in Stage 1 by Treatment Group Cox Proportional Hazards Regression	Stage 1 Modified Intent-to-Treat Set
	14.2.3.2.3	Analysis of Time to Change from Baseline in Myopia Progression of -0.75 D Normalized SER in Stage 1 by Treatment Group Cox Proportional Hazards Regression	Stage 1 Intent-to-Treat Set
14.2.3.3		New Prescriptions Given After the Start of Treatment due to Progression, at Month 36	
	14.2.3.3.1	Analysis of the New Prescriptions Given After the Start of Treatment due to Progression, at Month 36 Cochran-Mantel-Haenszel Test	Stage 1 Modified Intent-to-Treat Set

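### The new-prescription comparison (SAP 8.3.9 and 8.3.10) has no follow-up term and no rule for early leavers, so unequal dropout would bias this tertiary endpoint

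*SAP*

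**What the plan says.** SAP 4.3 (tertiary endpoints 9 and 10) defines the endpoint as the "difference in the mean number of new prescriptions given after the start of treatment due to progression through the Month 36 visit", once for 0.02% and once for 0.01% against vehicle.

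SAP 8.3.9 and 8.3.10 give one method for both comparisons, the "Cochran-Mantel-Haenszel row mean scores (ANOVA) statistic", with the request "tables Treatment*Prescriptions /cmh noprint". That request has no stratum variable, no exposure or offset term and no restriction to completers. The Index of Tables plans the output for the whole Stage 1 mITT and ITT sets under the title "Analysis of the New Prescriptions Given After the Start of Treatment due to Progression, at Month 36 Cochran-Mantel-Haenszel Test".

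SAP 6.3 sends missing efficacy data to the relevant part of section 8, but 8.3.9 and 8.3.10 do not mention the subject.

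The protocol synopsis (Number of Subjects) states: "The drop-out rate over the 3 years of the safety and efficacy stage of the study (Stage 1) is estimated to be 27"%, a single figure for all arms. The synopsis (Study Procedures, screening visit) makes a new prescription "applicable if the refraction reveals at least -0.50 D myopic progression and/or if the eye care practitioner deems it clinically necessary to improve vision". The Schedule of Procedures carries frames and lenses forward to later visits.

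**The concern.** A prescription for progression can be recorded only while a child attends for refraction. A child who leaves at Month 6 has had about one sixth of the opportunity of a child followed for 36 months. If both enter the table with a raw count, the early leaver's zero is treated as equal to three prescription-free years. The arm that loses more children then looks better. The error can run either way: heavier loss on active treatment can create an apparent benefit, and heavier loss on vehicle can hide a real one.

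The plan itself treats arm-related dropout as credible. Its tipping-point analysis of the primary endpoint (SAP 8.1.3) lists lack of efficacy, adverse events and withdrawn consent as treatment-related reasons for missing data. The neighbouring endpoint, time to -0.75 D (SAP 8.3.7), censors at the last Stage 1 visit and adjusts for age and baseline SER. The prescription count has neither protection.

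At stake is the reading of one tertiary result per dose.

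**Working it through.** **The plan's own figures.** Dropout: 1 - 0.9^3 = 0.271, matching 27%. Inflation: 91/0.73 = 124.7 and 136/0.73 = 186.3, against the stated 125 and 186. Exact Fisher power for 0.25 vs 0.07 is 95.6% (136 vs 91) and 90.1% (91 vs 91), against the stated 95% and 90%. No rate, power or effect size is given for new prescriptions, so only the arm sizes and pooled dropout carry over.

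**Inputs.** From the documents: 186 children on 0.02% and 125 on vehicle (mITT targets), 3 years, two-sided 5%. Assumed: rate r of 0.3 to 1.0 prescriptions per child-year; arm-specific dropout d, with leaving times uniform over 3 years and unrelated to progression; counts either Poisson (φ = 0) or overdispersed between children (gamma variance φ = 0.5).

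**Follow-up and counts.** Mean follow-up is E(t) = 3 - 1.5d, and E(t²) = 9 - 6d. The count has mean m = r·E(t) and variance v = r·E(t) + r²[(1 + φ)E(t²) - E(t)²].

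- Dropout 34% vs 17%: follow-up 2.490 vs 2.745 years, ratio 0.907. The active arm shows 9% fewer prescriptions with no drug effect.
- Dropout 17% active vs 34% vehicle, true rate ratio 0.8: expected count ratio 0.8 × 2.745/2.490 = 0.882.
- Dropout 23% active vs 30% vehicle, true rate ratio 0.8: 0.8 × 2.655/2.550 = 0.833.

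**Rejection rate of the planned test.** For two rows the statistic is the between-arm sum of squares divided by the overall variance s², referred to chi-square on 1 df. Approximately, z = |m_A - m_V| / √[s²(1/186 + 1/125)], and the rejection rate is Φ(z - 1.96) + Φ(-z - 1.96).

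Example: r = 0.7, φ = 0, no true effect, 34% vs 17%.
- Means: 0.7 × 2.490 = 1.743 and 0.7 × 2.745 = 1.9215, difference 0.1785.
- Variances: 1.743 + 0.49 × (6.96 - 6.200) = 2.115 and 1.9215 + 0.49 × (7.98 - 7.535) = 2.140.
- s² = (186 × 2.115 + 125 × 2.140)/311 + (186 × 125/311²) × 0.1785² = 2.133.
- z = 0.1785/√(2.133 × 0.013376) = 1.057, so the rejection rate is 18.4%.

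The same formula over r = 0.3 to 1.0 and φ = 0 or 0.5 gives the planned-test column below; simulation agrees to within about one percentage point. The offset column is simulated (log rate ratio on person-time, robust variance).

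| Dropout, 0.02% / vehicle | True rate ratio | Planned test rejects | With offset |
|---|---|---|---|
| 27% / 27% | 1.0 | 5% | 5% |
| 30% / 23% | 1.0 | 6–8% | 5% |
| 34% / 17% | 1.0 | 9–23% | 5% |
| 27% / 27% | 0.8 | 27–76% | 29–84% |
| 23% / 30% | 0.8 | 20–59% | 29–84% |
| 17% / 34% | 0.8 | 12–33% | 29–84% |

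The low ends are overdispersed counts at 0.3 per year; the high ends are Poisson counts at 1.0 per year. Pooled dropout at 34/17 is (186 × 0.34 + 125 × 0.17)/311 = 27.2%, close to plan. At 17/34 it is 23.8%, below plan.

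With exponential leaving times and a 20% vs 37% split, Poisson counts give 13 to 28% false positives over the same rates. At 0.5 per year that setting gives 17.6% for 0.02% vs vehicle and 14.4% for 0.01% vs vehicle (125 per arm).

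**The case against.** Most of the opposing case concerns weight, and much of it stands.

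- **No confirmatory claim depends on this.** The fixed sequence covers only the primary and secondary endpoints (SAP section 8). A reader might infer that the efficacy conclusion or its type I error is at risk. The documents do not support that.
- **The harm needs unequal dropout.** The documents give one pooled figure and no arm-specific forecast. A reader might infer that bias is expected. It is only possible: with equal dropout the test is valid, and at a moderate gap the distortion is small.
- **The SAP does not say that early leavers score zero.** That is the natural reading of a full-set count table. However, the text counts through Month 36 while the table title says at Month 36. The certain defect is the missing rule and missing follow-up term.
- **There is partial mitigation.** Children who stop medication are to remain in follow-up to Month 36 (Protocol, Withdrawal of Subjects), so only lost visits shorten the count. For these children, though, only the 12-month visits are called essential. The time-to-event result in 8.3.7 offers a cross-check.
- **The absent strata are a lesser matter.** A reader might blame the unstratified table for the bias. Leaving out age and SER costs precision and consistency with the randomisation; adding them would not remove a dropout bias.
- **An offset is not a full cure.** If vehicle children leave because they progress fast, dropout is informative. With leaving tied to a child's own rate (about 17% vs 31 to 34%) and a true ratio of 0.80, the offset gives roughly 0.83 to 0.88 and raw counts roughly 0.93 to 0.97. The offset is better but still biased towards no effect.

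None of this defends the test as specified. It limits how much the point matters.

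**Conclusion.** The point holds as a minor but specific improvement. As written, the comparison treats unobserved time as prescription-free and is biased whenever follow-up differs between arms. The distortion is nil for size at equal dropout, slight at a seven-point gap and material at a two-fold imbalance, where a true 20% reduction could also be largely hidden. These magnitudes rest on assumed prescription rates, arm-specific dropout, dispersion and non-informative leaving times, none of which the documents supply. Even with equal dropout, the offset analysis has slightly more power. The planned statistic also yields a p-value without an effect estimate or interval, although the endpoint is defined as a difference in means.

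**What to change.** Replace the test in SAP 8.3.9 and 8.3.10 with a negative binomial model, or a Poisson model with robust variance. Use log follow-up time to the last Stage 1 visit as offset, and treatment, age stratum and SER stratum (as randomized) as factors. Report rate ratios with 95% confidence intervals for 0.02% and 0.01% versus vehicle. State that early leavers contribute their prescriptions and observed time up to their last Stage 1 visit, and align the table title with the text on through versus at Month 36.

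The cost is a few lines of SAP wording and one procedure call, with no new data. The downsides are an assumed form of dispersion, a roughly constant rate over three years, and residual bias if dropout depends on a child's own progression. That last limit should be stated beside the result.

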#### **Sample Size:**

#### **Atropine Sulfate Ophthalmic Solution, 0.02%:**

A Fisher's exact test with a 0.05 two-sided significance level will have 95% power to detect the difference between an Atropine Sulfate Ophthalmic Solution, 0.02% responder proportion of 0.25 and a Vehicle responder proportion of 0.07 when the sample sizes are 136 and 91, respectively.

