# **Atropine Sulfate Ophthalmic Solution, 0.01%:**

A Fisher's exact test with a 0.05 two-sided significance level will have 90% power to detect the difference between an Atropine Sulfate Ophthalmic Solution, 0.01% responder proportion of 0.25 and a Vehicle responder proportion of 0.07 when the sample size in each group is 91.

**Table 2:** Schedule of Procedures

Assessment  Visit Number  Month	Screening Baseline a	Treatment Stage 1 (Office Visits Every 3 Months and Telephone Checks a ± 2 Weeks)															ll .	Treatment Stage 2 (Every 3 Months ± 2 Weeks)				
	1	T1	T2	3	Т3	3	T4	4	T5	5 12	6	7 18	8 21	9	10 27	11	12	13	14 39	15 42	16 45	17 48 (EOS) b
	0		2		4.5	6	7.5	9	10.5		15			24		30	33	3 36 (EOS) b				
Informed consent/assent c	X																					
Demographics/medical/ocular history	X																					
Prior/concomitant medication	X																					
Urine pregnancy test d	X																					
Re-consent/re-assent e																		X	X	X	X	X
Modified ATI questionnaires (QoL)																				Xef		Xef
Height and weight	X									X				X				X				X
Heart rate	X					X				X		X		X		X		X		X		X
Best-corrected visual acuity £g	X					X				X		X		X		X		X		X		X
Pupil size measurement (photopic)	X					Х				X		Х		X		X		X		X		X
Slit-lamp examination	X					X				X		X		X		X		X		X		X
Intraocular pressure	X					X				X		X		X		X		X		X		X
Dilated fundus examination	X									X				X				X				X
Cycloplegic autorefraction	X					X				X		X		X		X		X		X		X
Inclusion/exclusion criteria assessment	X																					
Randomization/re-randomization (M 36)	X																	X				
Axial length	X					Х				X		X		X		X		X		X		X
Crystalline lens thickness (where feasible)	X					Х				Х		X		X		Х		X		X		X
Collect study medication materials				X		X		Х		X	Х	X	X	X	X	X	Х	X	X	X	X	X

IND 130341

Assessment	Screening Baseline a		Treatment Stage 1  (Office Visits Every 3 Months and Telephone Checks a ± 2 Weeks)												Treatment Stage 2 (Every 3 Months ± 2 Weeks)							
Visit Number	1	T1	T2	2	Т3	3	T4	4	T5	5	6	7	8	9	10	11	12	13	14	15	16	17
Month	0	1	2	3	4.5	6	7.5	9	10.5	12	15	18	21	24	27	30	33	36	39	42	45	48
																		(EOS)b				(EOS)b
Concomitant medication review				Х		Х		Х		X	X	X	X	X	X	X	X	X	X	X	X	X
Adverse event assessment	X	X	X	X	X	X	X	X	X	X	X	X	X	X	X	X	X	X	X	X	X	X
Dispense study medication (frames/lenses) gh	Х			X		Х		X		X	X	X	X	X	X	X	X	X	X	X	X	

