### **3.6. Treatment Assignment & Blinding**

#### **3.6.1. Stage 1**

In Stage 1, subjects will be randomized in a 2:2:3 ratio of vehicle: Atropine Sulfate Ophthalmic Solution, 0.01%: Atropine Sulfate Ophthalmic Solution, 0.02%. The target number of subjects to be randomized into the 6- to 10-year age group (436), the primary efficacy population, will be:

- Vehicle (placebo): 125
- Atropine Sulfate Ophthalmic Solution, 0.01%: 125
- Atropine Sulfate Ophthalmic Solution, 0.02%: 186

Approximately 483 subjects over all eligible ages will be enrolled, resulting in the following numbers of subjects in each arm:

- Vehicle (placebo): 138
- Atropine Sulfate Ophthalmic Solution, 0.01%: 138
- Atropine Sulfate Ophthalmic Solution, 0.02%: 207

This document is confidential.

The randomization will be stratified twice: (1) by age at randomization (subjects < 9 years; subjects ≥ 9 years) and by (2) refractive error (less myopic: SER -0.50 to -3.00 D; more myopic: one or more eyes with SER -3.01 to -6.00 D). The stratification is used to balance these characteristics across the 3 treatment groups. Enrollment will proceed until 436 subjects aged 6 to 10 years have been randomized and at least 483 subjects overall have been randomized. Enrollment may be closed to subjects ≥ 11 years following enrollment of 50 subjects in this age group to avoid over-enrollment into the study.

If subjects meet eligibility criteria at the Screening/Baseline visit (Day 0), subjects will be randomly assigned to masked study medication. Study sites will utilize the IRT to assign kits to subjects. The treatment kit number will be recorded in the subject's eCRF. Study medication from the Interactive Response Technology (IRT)-assigned kit will be dispensed to the subject/subject's parent or guardian for dosing that evening. Subjects will return to the study site at 3-month intervals to return their study medication and their next assigned study medication kit will be dispensed. It is preferred that the subject attend every visit, but the parent/guardian may attend a 3-month visit without the subject if necessary. Both the subject and parent/guardian must be present at all 6-month safety and efficacy visits.

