## 4. Endpoints

### 4.1. Primary Efficacy Endpoint

The primary efficacy endpoint is the overall between-treatment group (Atropine Sulfate Ophthalmic Solution, 0.02% versus Vehicle) difference in the proportion of subjects' eyes who show less than 0.5 D myopia progression (SER) from baseline at the Month 36 visit.

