## 8. Efficacy

The primary and all secondary endpoints comprise a fixed sequence set of endpoints to be tested in the order given below. All statistical testing will be performed using a two-sided testing procedure with  $\alpha=0.05$ . Summaries of change for Stage 2 will include change from baseline and change from Stage 2 baseline (Month 36).

The order for the fixed sequence of endpoints to be tested are:

1. Between-treatment group (Atropine Sulfate Ophthalmic Solution, 0.02% versus Vehicle) difference in the proportion of subjects' eyes who show less than 0.5 D myopia progression (SER) from baseline at the Month 36 visit. (Primary Endpoint)
2. Between-treatment group (Atropine Sulfate Ophthalmic Solution, 0.02% versus Vehicle) difference in the mean change from baseline in SER at the Month 36 visit.
3. Between-treatment group (Atropine Sulfate Ophthalmic Solution, 0.01% versus Vehicle) difference in the proportion of subjects' eyes who show less than 0.5 D myopia progression (SER) from baseline at the Month 36 visits.
4. Between-treatment group (Atropine Sulfate Ophthalmic Solution, 0.01% versus Vehicle) difference in the mean change from baseline in SER at the Month 36 visit.
5. Between-treatment group (Atropine Sulfate Ophthalmic Solution 0.02% versus Vehicle) difference in the mean change from baseline in axial length at the Month 36) visit,
6. Between-treatment group (Atropine Sulfate Ophthalmic Solution 0.01% versus Vehicle) difference in the mean change from baseline in axial length at the Month 36 visit.

Not all sites used the same Vertex distance (VD) in mm when measuring refraction with autorefractor. All averaged SER measurements for each participant used in tables and analyses will be normalized to a VD of 0 mm to the corneal plane. The normalization (Fannin 1987) will be applied using

$$\text{Normalized SER} = \frac{100}{\frac{100}{\text{SER}} - \frac{\text{VD}}{10}}$$

where SER is the original SER from CRF.

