8.3.12. Between-treatment Group (Atropine Sulfate Ophthalmic Solution, 0.01% versus Vehicle) Difference in the Proportion of Subjects who Progressed to High Myopia (SER -6.00 D or more myopic) at the Month 36 Visit

A tertiary analysis will be performed on the between-treatment group (Atropine Sulfate Ophthalmic Solution, 0.1% versus vehicle) difference in the proportion of subjects who progressed to high myopia (SER -6.00 D or more myopic) at the Month 36 visit. Progression to high myopia is defined as either of a subject's eyes progressed to high myopia at any time during a visit window.

Results will be presented as results and by baseline myopia stratification. The overall analysis will be performed using a Mixed Model based on the binomial distribution using a logit link function. Progression as the dependent variable, subject, treatment, visit, and baseline age group (as randomized) and SER (as randomized) as independent variables, treatment by visit, treatment by SER (as randomized) and treatment by visit by SER (as randomized) interaction terms included. Random intercepts for subject will be included using variance components. The analysis will be performed using the mITT analysis set assuming data is missing at random.

```
proc glimmix data=master empirical method=quad;  
  class subjid trtpn(ref='0') avisitn agegrp1 sergrp1;  
  model eff(event='1') = trtpn avsitn agegrp1 sergrp1 trtpn*avisitn trtpn*sergrp1 trtpn*avisitn*sergrp1 /  
  dist=bin link=logit solution or;  
  random intercept / subject=subjid type=vc;  
  estimate '0.02% vs. Pbo Month 36' trtpn 0 1 -1 trtpn*avisitn 0 0 0 0 0 0 0 0 0 0 0 0 1 0 0 0 0 0 -1;
```

This document is confidential.

*estimate '0.02% vs. Pbo Month 36 Low ' trtpn 0 1 -1 trtpn\*avisitn 0 0 0 0 0 0 0 0 0 0 0 0 1 0 0 0 0 0 -1  
trtpn\*avisitn\*blmymop 0 1 0 0 0 0 0 -1 0;*

*estimate '0.02% vs. Pbo Month 36 High ' trtpn 0 1 -1 trtpn\*avisitn 0 0 0 0 0 0 0 0 0 0 0 0 1 0 0 0 0 0 -1  
trtpn\*avisitn\*blmymop 0 1 0 0 0 0 0 -1;*

Summary statistics will be presented along with a full data listing by treatment group.

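### The high-myopia model in SAP 8.3.11/8.3.12 carries stratum interactions for an event few less-myopic children can reach, so its low-stratum and overall Month 36 odds ratios may well have no finite estimate, and no fallback is planned

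*SAP*

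**What the plan says.** SAP 8.3.11 (0.02%) and 8.3.12 (0.01%) compare each dose with Vehicle on the proportion of children with either eye at -6.00 D or worse at Month 36. Section 8.3.11 takes its method from 8.3.12 and adds: "Results will be presented as overall results and by baseline myopia stratification".

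The model in 8.3.12 is a binomial mixed model with a logit link. Its main effects are treatment, visit, age group and SER group, with a random intercept for subject and "treatment by visit, treatment by SER (as randomized) and treatment by visit by SER (as randomized) interaction terms included". The code requests quadrature likelihood and the EMPIRICAL (sandwich) covariance option. It has no penalty term, and the section names no exact method, reduced model or rule for non-convergence.

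The SER strata in SAP 3.6.1 are "less myopic: SER -0.50 to -3.00 D; more myopic: one or more eyes with SER -3.01 to -6.00 D". SAP 8 says that the SER values used in analyses "will be normalized to a VD of 0 mm to the corneal plane", and that stratification uses the values as measured.

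**The concern.** The three-way term gives every arm, visit and stratum combination its own logit. With 3 arms, 6 visits and 2 strata that is 36 cells. By definition the less myopic stratum starts at least 3.0 D short of the event. If one of two compared arms has no low-stratum event at Month 36, maximum likelihood has no finite low-stratum odds ratio. An overall contrast from the same model has to combine both strata, so it inherits the problem even though the more myopic stratum holds usable events.

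At stake is the trial's answer on preventing high myopia (tertiary endpoints 11 and 12). The less visible danger is that the program does not fail. It may print an extreme overall odds ratio with a small standard error, because the sandwich estimate need not grow as the coefficient diverges.

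**Working it through.** **1. The plan's own figures.** The Protocol's Sample Size section states: "A Fisher's exact test with a 0.05 two-sided significance level will have 95% power to detect the difference", with a 0.02% "responder proportion of 0.25 and a Vehicle responder proportion of 0.07 when the sample sizes are 136 and 91, respectively". For 0.01% it assumes "a Vehicle responder proportion of 0.07 when the sample size in each group is 91", with 90% power. Exact enumeration of Fisher's test gives 95.6% (136 versus 91) and 90.1% (91 versus 91), so these inputs reproduce. No power or event rate is stated for high myopia.

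**2. Distance to the event.** The formula in SAP 8 is normalised SER = 100/(100/SER - VD/10).
- At a vertex distance of 0, a child at -3.00 D needs 3.00 D.
- At an assumed 12 mm, -3.00 D becomes 100/(-33.33 - 1.2) = -2.90 D, so the child needs 6.00 - 2.90 = 3.10 D on the analysis scale.
- A child who enters at -0.50 D needs about 5.5 D.

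**3. Calibrating progression.** The plan counts as a responder the "proportion of subjects' eyes who show less than 0.5 D myopia progression (SER) from baseline at the Month 36 visit", with 7% assumed on Vehicle and 25% on active. If progression is normal, the mean is 0.5 + 1.476 x SD on Vehicle and 0.5 + 0.674 x SD on active. At SD 0.8 D these are 1.68 D and 1.04 D. The SD is not in the documents and is varied from 0.6 to 1.2 D.

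**4. Chance of an empty Month 36 cell, one eye per child.** Assumptions: baseline SER uniform over the stratum, 12 mm, and 70% of completers in the low stratum (0.70 x 91 = 64 Vehicle; 0.70 x 136 = 95 on 0.02%). With event probabilities p_V and p_A,

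P(at least one empty) = 1 - [1 - (1 - p_V)^64] x [1 - (1 - p_A)^95].

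| SD (D) | p_V | p_A | Expected events (Vehicle / 0.02%) | P(at least one empty) |
|---|---|---|---|---|
| 0.6 | 0.02% | about 0 | 0.01 / 0.00 | >99.9% |
| 0.8 | 0.5% | 0.05% | 0.33 / 0.05 | 99% |
| 1.0 | 2.8% | 0.4% | 1.8 / 0.4 | 72% |
| 1.2 | 7.3% | 1.5% | 4.7 / 1.4 | 24% |

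**5. Either eye, as 8.3.12 defines the event.** Further assumptions: the first eye is uniform over the stratum; the second differs from it by a normal amount with SD 0.35 D, held inside the stratum; and progression correlates 0.9 between eyes. With 60-75% of children in the low stratum and a vertex distance of 0 or 12 mm, the chance is about 93-100% at SD 0.6-0.8 D, 44-61% at 1.0 D and 7-16% at 1.2 D.

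**6. Bunched baselines (one eye, 12 mm, 70% share).** If every low-stratum child sat at -3.00 D, the chance would be 99.9%, 66%, 8% and 0.1% at SD 0.6, 0.8, 1.0 and 1.2 D.

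**7. What an empty cell does.** One simulated Month 36 dataset had 1/48 low-stratum events on Vehicle and 0/99 on 0.02%. It was fitted with treatment, stratum and their interaction; random intercept and age were left out, and neither would give an empty cell a finite estimate.

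| Contrast (log odds ratio) | 5 iterations | 25 iterations | Model SE at 25 | Sandwich SE at 25 |
|---|---|---|---|---|
| Low stratum | -2.71 | -22.72 | 35,792 | 1.02 |
| Overall, equal weights | -2.31 | -12.31 | 17,896 | 0.58 |
| High stratum | -1.90 | -1.90 | 0.57 | 0.57 |

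The overall value is the mean of the two strata: (-22.72 - 1.90)/2 = -12.31. Divided by the sandwich SE, it gives z = -12.31/0.582 = -21.2, which is an artefact.

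**8. Without the stratum interaction.** In the same dataset the overall log odds ratio is -1.98 (SE 0.56). In 400 simulated trials per setting (SD 0.6-1.2 D, low-stratum share 50% or 70%), neither Vehicle nor 0.02% ever had zero Month 36 events in total, and neither had an empty high-stratum cell at Month 36.

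**The case against.** A reader might infer that these odds ratios cannot be estimated at all. The documents do not support that. Failure needs zero Month 36 low-stratum events in a compared arm, and whether that happens turns on an SD, a baseline distribution and stratum shares that are not given. At SD 1.2 D, or with baselines near -3.00 D and an SD of 1.0 D or more, a finite though imprecise estimate is the likelier outcome. Counting one eye instead of either eye also overstates the risk: 72% at SD 1.0 D in step 4 against 44-61% in step 5.

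Two other figures can mislead. On average 15 to 22 of the 36 cells are empty in the step 8 simulations, but these are not all Month 36 cells. Empty cells at earlier visits threaten convergence without making the Month 36 contrast infinite. And a normalised -6.00 D is a measured -6.47 D at 12 mm, which suggests a bar raised by 0.47 D. Baseline is normalised too, so the required progression rises only from 3.00 to 3.10 D.

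Finally, the endpoint is tertiary, and SAP 8.3.11 and 8.3.12 already call for summary statistics and a full listing, so descriptive results survive a failed model. All of this stands. It limits the claim to a conditional one. It does not supply the missing fallback or remove the risk of a falsely precise result.

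**Conclusion.** The concern holds as a conditional one. Low-stratum Month 36 events will be few. If a compared arm has none, the planned model has no finite low-stratum odds ratio, and an overall odds ratio averaged over the strata diverges with it. Counting either eye, that is close to certain at a progression SD of 0.6-0.8 D, about even at 1.0 D and unlikely but not negligible at 1.2 D. These figures rest on normal progression calibrated to the planned responder rates, uniform baseline SER, 60-75% of children in the low stratum, a vertex distance of 0 or 12 mm, and the between-eye assumptions in step 5; none of these except the responder rates comes from the documents.

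A reader should not carry the point further up the plan. High myopia is outside the six-step fixed sequence in SAP 8, so no alpha and no primary or secondary conclusion depends on it. The change is worth making because it is cheap and the wrong output could look convincing.

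**What to change.** Amend SAP 8.3.11/8.3.12 before Stage 1 unblinding:

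- **Overall Month 36 odds ratio:** drop treatment-by-SER and treatment-by-visit-by-SER. Keep treatment, visit, age group, SER group, treatment-by-visit and the subject random intercept.
- **Stratum odds ratio:** fit a model in the -3.01 to -6.00 D stratum only.
- **Less myopic stratum:** report counts with exact intervals.
- **Fallback:** if the model does not converge or a compared arm has no events, use a Month 36 Firth logistic model or a stratified exact analysis, chosen now. The convergence trigger is needed because early arm-by-visit cells can be empty in the reduced model too.

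The cost is SAP wording and simpler code. The trial gives up a model-based odds ratio for the less myopic stratum, and the overall result assumes a common odds ratio across strata. The fallback uses only children observed at Month 36. At the planned 27% drop-out, about 0.27 x 436 = 118 children in the primary age group would be lost to it, along with the repeated-measures analysis under missing at random. It should therefore stay a fallback and not replace the model.
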